3.3.2 Follow-up for withdrawn subjects

N/A

4.0 Recruitment Methods

4.1 Identification of subjects

We will recruit through a parent letter placed in each child's mailbox. Any children enrolled in the childcare center, along with their parents, may participate. A trained staff member will be at the childcare center at the time of child drop off and/or pick up to explain this study.

Teachers will be recruited verbally in the classrooms of participating children.

4.2 Recruitment process

We will recruit through a parent letter placed in each child's mailbox. A member of our lab approved to do recruitment and consenting of subjects will be available in the center for an evening during child pick up to answer any questions parents may have.

Teachers in classrooms will be asked to participate verbally by study staff.

4.3 Recruitment materials

Parents will receive a letter in their child's mailbox that will describe the study. The consent form will be included with the letter.

Teachers in classrooms will be asked to participate verbally by study staff. A consent form will then be reviewed and signed by each teacher willing to participate.

4.4 Eligibility/screening of subjects

Children with allergies to foods served will not be eligible to participate in this study. Screening questions regarding food allergies and intolerances will be included with the consent form.

5.0 Consent Process and Documentation

5.1 Consent Process

Participation in this study is voluntary.

5.1.1 Obtaining Informed Consent

5.1.1.1 Timing and Location of Consent

Consent will be signed by the parent. Consent will be obtained at the childcare center with a trained member of the lab staff present.

Teachers will consent prior to the first study week in their classroom at the childcare center to fill out questionnaires about children enrolled.

5.1.1.2 Coercion or Undue Influence during Consent

Parents will be given consent form to take home to review on their own and can decide if they want their child to participate.

Teachers will be given the opportunity to review the consent form on their own and can decide if they wish to participate.

5.1.2 Waiver or alteration of the informed consent requirement

N/A

5.2 Consent Documentation

5.2.1 Written Documentation of Consent

Participation in this study is voluntary.

Participants' parents will sign the consent form. Two copies of the consent form will be given, one to be signed and returned to study staff, one to be kept for parents' records.

Teachers will sign a separate consent form for their participation and will be given a copy for their own records.

5.2.2 Waiver of Documentation of Consent

For addendum consent – taking the packed meal(s) implies consent.

5.3 Consent – Other Considerations

5.3.1 Non-English Speaking Subjects

It is not anticipated that there will be any non-English speaking or illiterate subjects.

5.3.2 Cognitively Impaired Adults

5.3.2.1 Capability of Providing Consent

N/A

5.3.2.2 Adults Unable To Consent

N/A

5.3.2.3 Assent

N/A

5.3.3 Subjects who are not yet adults (infants, children, teenagers)

5.3.3.1 Parental Permission

Parents will sign consent for their child to participate. Two copies of the consent form will be given, one to be signed and returned to study staff, one to be kept for parents' records.

5.3.3.2 Assent

A child can refuse to eat any meal if he/she chooses. Before height and weight is measured or the Tasting Game occurs, children are asked if they want to do it and can refuse to participate.

6.0 Study Design and Procedures

6.1 Study Design

This study will have a within-subjects crossover design with repeated measures across five days of meals and three experimental conditions. The investigators will vary the proportions of low-energy-dense vegetables and fruits served at meals by either addition or substitution. In the three experimental conditions, the same foods will be served - only the amounts and proportions of foods will be varied. In the Baseline condition, typical proportions of age-appropriate foods will be served. In the Addition condition, the portion sizes of low-energy-dense vegetables and fruits will be increased, and in the Substitution condition, the portions of low-energy-dense vegetables and fruits will be increased by replacing an equivalent weight of foods higher in energy density. The order of the conditions across the three experimental periods, as well as the order of the five menus within each five-day period, will be counterbalanced by classroom. The three five-day experimental periods will be separated by a two-week washout period. All menus in all conditions will meet the minimum requirements of the United State Department of Agriculture (USDA) Child and Adult Care Food Program (CACFP) [3].

6.2 Study Procedures

1. Over five consecutive days, enrolled children will be served breakfast, lunch, dinner, and snacks of foods commonly served in the childcare center following their regular meal and snack schedules - menus were developed from the menus at the childcare centers to be as similar as possible to the foods that children are regularly served. Milk or water will be served as beverages. Meals will be served at tables of three to six children and one adult, which is a standard practice at the childcare centers. The adults at the table will be instructed not to discuss the food or to encourage the children to eat. There will be three conditions, with changes only in the proportion of lower-energy-dense vegetables and fruits at the meals. Each participant will be served an individual pre-weighed meal. All food and beverage items will be weighed with a food scale before and after meals and snacks to within 1 gram in order to determine the amount consumed. Participants will be told they can eat as much or as little of the foods as they would like. Trained observers (research personnel) will document food and beverage spillage and any comments made about the food. The children will be provided with an evening snack pre-packaged for consumption at home. Any leftover food from the evening snack will be returned to the childcare center the following day to be weighed.
2. In the event of extenuating circumstances (e.g. unexpected childcare center closure, inclement weather) the researchers may decide to pack out a meal, or meals, which can be consumed outside of the childcare center. Participants will be notified in advance if this should occur. Any leftover food from a packed meal, or meals, will be returned to the childcare center the following day to be weighed. Applicable instructions for serving or reheating will be provided.
3. Parents will be asked not to serve any additional food or beverages to their child apart from those provided by the study and water. If the participant deviates from the procedure and consumes extra food, the estimated food and beverage consumption will be requested.
4. Physical activity levels will be measured over the five consecutive days using triaxial accelerometers. The accelerometers will be worn while the children are present at the childcare center (from before breakfast to after dinner). Research staff will attach a device to the child's waist upon arrival at the center each morning and remove the device upon the child's departure from the center each evening.
5. On the 16th visit to the childcare center, children will have their height and weight measured by a trained staff member of the lab. Body weight will be measured in triplicate using a portable digital scale. Height will be measured in triplicate using a portable stadiometer. The children will also complete the Tasting Game. They will be given small samples of foods served in the study and asked to point to a cartoon face that represents their liking of the food on a scale of yucky to

yummy. Children will also look at three plates (one from each condition) from two meals and be asked which they would prefer.

6. Parents will be asked to complete an Evening Report Form, Background Questionnaire, the Children's Eating Behavior Questionnaire, the Caregiver's Feeding Style Questionnaire, and the Child Feeding Questionnaire. The Evening Report Form will be completed at the end of each study day and returned each morning to research personnel. All questionnaires (the Background Questionnaire, Children's Eating Behavior Questionnaire, Caregiver's Feeding Style Questionnaire and Child Feeding Questionnaire) will be administered during the last five days of the study. All questionnaires will be completed via pencil and paper.
7. Photos of children eating, participating in the tasting game, and having their height and weight measured may be taken.
8. There will be a minimum of a one-week break between study weeks. There will be a four- to six-week wash-out period between running this and any previous experiments at each childcare center.
9. Approved lab staff (on this IRB application) will email parents the Friday before a study week to remind parents of the start of the study.
10. Teachers will be asked to answer two questionnaires (Caregiver's Feeding Style Questionnaire, Children's Eating Behavior Questionnaire) per child in their classroom. Teachers will only complete questionnaires about children who are enrolled in the study. This questionnaire will be administered by paper and pencil. Teachers will be verbally told by study personnel which child to answer each questionnaire about.
11. Data from questionnaires completed by teachers will be linked to child participants by a three-digit number and letter only.

6.3 Duration of Participation

The duration of the study will be five consecutive days, and each participant will be asked to complete three of these five-day periods. Within each day, each meal and snack will take approximately 30 minutes to complete. The estimated time required by the participant each day is 2.5 hrs. The estimated total time required for all of the meals is 37.5 hours. The height and weight measurements and the Tasting Game on the final visit after the 15 days are completed will require an additional hour of time. For the parents, another 30 minutes will be requested to complete the questionnaires. The total time commitment for the study is 39 hours. Teachers will spend approximately 20 minutes per questionnaire.

7.0 Statistical Plan

7.1 Sample size determination

The sample size for the study was based on the statistical power to detect differences in energy intake between the Baseline and Substitution conditions across study days. The sample size was estimated from a linear mixed model and an approximation technique [4] using exemplary data sets based on our previous five-day studies in preschool children [1,2]. We assumed that the minimum clinically significant difference in energy intake across days was 50 kcal, which is about 5% of daily intake for a typical preschool child. To detect this change over time with a Type 1 error rate of 5% and power of 90%, it was determined that 48 participants would be required. To allow for withdrawals and non-compliance to the protocol, 55 to 60 children will be enrolled.

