7.2 Statistical methods

The study hypotheses will be assessed using linear mixed models with repeated measures. Differences in mean outcomes will be tested across the three experimental conditions of the proportion of vegetables and fruits served in meals, as well as across the five days of intake.

Hypotheses 1 and 2 test whether variations in the proportion of low- and high-energy-dense foods influence the mean daily outcomes of energy intake, food and beverage intake, and energy density. To test these hypotheses, the fixed factors in the models will be condition, study week, study day, menu, childcare center, classroom, and sex. Interactions between these factors will be tested and removed from the model if not significant and participants will be treated as a random effect. The Tukey-Kramer method will be used to adjust for multiple pairwise comparisons between means. The energy content of parentally reported non-study food consumption will be estimated by research staff. Daily energy intake will be analyzed both with and without the non-study items.

Hypothesis 3, concerning whether daily energy intake in the three conditions converges over each five-day period, tests whether regulation of energy intake occurs over time in response to variations in the proportion of low- and high-energy-dense foods served. To test this hypothesis, a random coefficients model will be used. The trajectories of intake over time will be allowed to vary randomly across subjects; thus, they will be modeled separately for each child. Time (study day) will be treated as a continuous covariate in the model and polynomial factors of time (linear and quadratic coefficients) will be tested as both fixed and random effects to determine the shape of the intake trajectory. The intercept of the trajectory will reflect the magnitude of daily intake at Day 1

and the linear coefficient will represent the rate of change in intake (slope) across time after Day 1. The quadratic coefficient, if significant, will represent the rate of acceleration or deceleration in intake (curvature) across time after Day 1.

It has been predetermined that children who have incomplete intake measures on ≥ 3 days in all 3 conditions will be excluded from analysis. It has also been predetermined that children who eat $>95\%$ of the food weight served on at least 1 day will be classified as “plate cleaners”, and their influence on the results will be tested.

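### Does the 90% power at 48 children in Section 7.1 fail to hold once the Tukey-Kramer adjustment in Section 7.2 is applied?

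*Combined protocol and SAP*

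**What the plan says.** Section 7.1 bases the sample size on the "statistical power to detect differences in energy intake between the Baseline and Substitution conditions across study days". It takes it that the "minimum clinically significant difference in energy intake across days was 50 kcal, which is about 5% of daily intake", and concludes that, "with a Type 1 error rate of 5% and power of 90%, it was determined that 48 participants would be required". The number came from a linear mixed model with exemplary data built from the group's earlier five-day studies. No standard deviation, within-child correlation, critical value or sidedness is reported. The section adds: "To allow for withdrawals and non-compliance to the protocol, 55 to 60 children will be enrolled".

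Section 7.2 has three conditions and states: "The Tukey-Kramer method will be used to adjust for multiple pairwise comparisons between means". It describes the target of the main models this way: "Hypotheses 1 and 2 test whether variations in the proportion of low- and high-energy-dense foods influence the mean daily outcomes of energy intake". The significance threshold is p < 0.05, again without sidedness. Hypothesis 3 (convergence over days) has a separate random coefficients model, for which no Tukey-Kramer adjustment is mentioned.

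**The concern.** The sample size is tied to one of three pairwise contrasts, and the analysis adjusts those contrasts for multiplicity. With three means, Tukey-Kramer requires a two-sided p-value of roughly 0.019 on a single contrast, not 0.05. A calculation that used a plain 5% would overstate the power of the test actually planned. Section 7.1 mentions no multiplicity allowance, so a reader may well suspect that this happened.

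90% is the only power figure in the plan. It belongs to a primary endpoint and to a difference that the investigators call the smallest that matters clinically. If the suspicion were right and only 48 children were analysed, a true 50 kcal difference would be missed about 19% of the time instead of 10%.

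**Working it through.** **Inputs.** From Section 7.1: 48 children, 90% power, 5% Type 1 error, 50 kcal, enrolment of 55 to 60. From Section 7.2: three conditions, Tukey-Kramer.

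**Can 48 be reproduced?** No, because neither the standard deviation (SD) nor the correlation is given. The SD can only be solved backwards. Under a normal approximation, the SD of a child's Baseline-Substitution difference is 50 × √48 / (critical value + 1.282):

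- two-sided unadjusted 5%: 346.4 / (1.960 + 1.282) = 106.9 kcal
- Tukey-adjusted 5%: 346.4 / (2.344 + 1.282) = 95.6 kcal

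Both SDs give exactly 48 children at 90% power. The documents give no means of choosing between them.

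**If the 5% was two-sided and unadjusted.** The SD cancels. The standardised effect at 48 is 1.960 + 1.282 = 3.242. The Tukey critical value for three means is q(0.95; 3, ∞)/√2 = 2.344. Power for the adjusted test is Φ(3.242 × √(n/48) − 2.344):

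| Children analysed | Standardised effect | Power |
|---|---|---|
| 48 | 3.242 | Φ(0.898) = 81.5% |
| 55 | 3.470 | Φ(1.126) = 87.0% |
| 60 | 3.624 | Φ(1.280) = 90.0% |

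With the noncentral t in place of the normal, power at 48 is 80.9% (47 df), 81.2% (94 df) or 81.5% (600 df). About 60 to 61 children would be needed for 90%. The difference detectable at 90% with 48 is 50 × (2.344 + 1.282)/3.242 = 55.9 kcal. Taking daily intake as 50/0.05 = 1,000 kcal, that is 5.6% of intake instead of 5%.

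**Other readings that Section 7.1 leaves open.**

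- *Family-wise 5%:* 90% at 48, as stated.
- *One-sided unadjusted 5%:* standardised effect 1.645 + 1.282 = 2.926; power at 48 is Φ(2.926 − 2.344) = 72.0%, or 70.7% with 47 df.
- *Overall condition test on 2 df:* at 94 df, 90% power needs a noncentrality of 13.07. With Addition midway between the other two, the pairwise standardised effect is √13.07 = 3.615, and adjusted power is about 89%. With Addition equal to Baseline it is √(0.75 × 13.07) = 3.131, and adjusted power is about 77%. It is lower still if Addition lies above Baseline.
- *A trajectory over days:* Section 7.1 also speaks of a change over time. None of these figures would then apply, since no Tukey-Kramer adjustment is stated for that model.

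**The case for a change.** The strongest case for acting is that the 50 kcal is expressed as a share of daily intake. That points to a mean difference, and a two-sided, unadjusted 5% is a natural default. On that footing the miss rate at 48 nearly doubles. The enrolment margin is no full answer, because Section 7.1 sets it aside for withdrawals and non-compliance; even with no losses, 55 children give about 87%. A few sentences in Section 7.1 would settle the question at little cost.

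The arithmetic stands, and so does the observation that Section 7.1 is silent. What does not stand is the step from silence to error. Nothing in Section 7.1 or 7.2 says the 5% was unadjusted. A mixed-model calculation on exemplary data could have used an adjusted contrast, an unadjusted contrast or the overall condition test. The 81% figure is therefore one conditional result among several; it is neither a best estimate nor a lower bound.

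The proposed wording would also change nothing that the trial does. The number of children, the model, the adjustment and the threshold all stay as they are.

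**Conclusion.** The gap is real but minor: Section 7.1 does not report which contrast, sidedness and critical value lie behind its 90%. No stated figure is shown to be wrong, and 48 can be neither confirmed nor refuted from the documents.

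On a two-sided, unadjusted pairwise reading, the shortfall at 48 is about 9 percentage points, falling to about 3 at 55 and to almost nothing at 60 if those numbers are analysed. On a family-wise reading there is none. The one-sided reading and some overall-test readings are less favourable, but the text supports them no better.

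Tukey-Kramer protects the family-wise error rate of the condition comparisons however the sample size was reached. The estimates and their confidence intervals do not depend on the planning alpha either. A non-significant Baseline-Substitution result would be judged from its interval against 50 kcal, not from the planned power. The concern therefore comes down to undocumented detail in a finished calculation, and the plan can stand.

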7.2 Statistical methods

The study hypotheses will be assessed using linear mixed models with repeated measures. Differences in mean outcomes will be tested across the three experimental conditions of the proportion of vegetables and fruits served in meals, as well as across the five days of intake.

Hypotheses 1 and 2 test whether variations in the proportion of low- and high-energy-dense foods influence the mean daily outcomes of energy intake, food and beverage intake, and energy density. To test these hypotheses, the fixed factors in the models will be condition, study week, study day, menu, childcare center, classroom, and sex. Interactions between these factors will be tested and removed from the model if not significant and participants will be treated as a random effect. The Tukey-Kramer method will be used to adjust for multiple pairwise comparisons between means. The energy content of parentally reported non-study food consumption will be estimated by research staff. Daily energy intake will be analyzed both with and without the non-study items.

Hypothesis 3, concerning whether daily energy intake in the three conditions converges over each five-day period, tests whether regulation of energy intake occurs over time in response to variations in the proportion of low- and high-energy-dense foods served. To test this hypothesis, a random coefficients model will be used. The trajectories of intake over time will be allowed to vary randomly across subjects; thus, they will be modeled separately for each child. Time (study day) will be treated as a continuous covariate in the model and polynomial factors of time (linear and quadratic coefficients) will be tested as both fixed and random effects to determine the shape of the intake trajectory. The intercept of the trajectory will reflect the magnitude of daily intake at Day 1

and the linear coefficient will represent the rate of change in intake (slope) across time after Day 1. The quadratic coefficient, if significant, will represent the rate of acceleration or deceleration in intake (curvature) across time after Day 1.

It has been predetermined that children who have incomplete intake measures on ≥ 3 days in all 3 conditions will be excluded from analysis. It has also been predetermined that children who eat $>95\%$ of the food weight served on at least 1 day will be classified as “plate cleaners”, and their influence on the results will be tested.

Analysis of covariance with linear mixed models will be used to test the influence on these outcomes of individual subject characteristics such as age, body mass index, and daily level of physical activity. Independent-samples t-tests will be used to assess differences in subject characteristics by sex and weight status (normal weight or overweight/obesity). Results will be considered significant at $p < 0.05$. All data will be analyzed using SAS software (SAS 9.4; SAS Institute, Inc.).

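### The Hypothesis 3 model in 7.2 lets trajectories vary by child but not by child and condition, has a linear term whose meaning changes if a quadratic is kept, does not carry over menu, and covers energy only

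*Combined protocol and SAP*

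**What the plan says.** Section 6.1 describes the design: "This study will have a within-subjects crossover design with repeated measures across five days of meals and three experimental conditions". Each child therefore has three sequences of five days. It also says that the order of conditions, "as well as the order of the five menus within each five-day period, will be counterbalanced by classroom".

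Section 7.2 introduces the convergence analysis as "Hypothesis 3, concerning whether daily energy intake in the three conditions converges over each five-day period". It names a random coefficients model with day as a continuous covariate, and describes the random part at the level of the child: "The trajectories of intake over time will be allowed to vary randomly across subjects; thus, they will be modeled separately for each child". Of the polynomial terms in day it says that the "linear and quadratic coefficients) will be tested as both fixed and random effects to determine the shape of the intake trajectory". The intercept is placed at Day 1, and "the linear coefficient will represent the rate of change in intake (slope) across time after Day 1". A quadratic term, if significant, is read as curvature.

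Menu appears only in the model for Hypotheses 1 and 2: "To test these hypotheses, the fixed factors in the models will be condition, study week, study day, menu, childcare center, classroom, and sex". In that model, "Interactions between these factors will be tested and removed from the model if not significant".

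Section 1.1 states Hypothesis 3 for vegetable, fruit and energy intake. The Hypothesis 3 paragraph of 7.2 mentions energy intake alone.

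**The concern.** Section 2.3 gives the regulation of intake over several days as the rationale of the study, and 7.2 says that Hypothesis 3 tests it. The answer is a comparison of slopes between conditions within the same child. Four features of the text affect that comparison.

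- **Error term.** Random slopes by child cancel when conditions are compared within a child. What remains is how far a child's slope differs from condition to condition. If such variation exists and has no term in the model, the standard error is wrong.
- **Linear coefficient.** Its stated meaning does not survive if the quadratic is kept. A reader could take the initial tangent for the trend over the week.
- **Menu.** Menu order is set by classroom, so menu and day are tied together within a classroom-week. The Hypothesis 3 paragraph does not mention menu.
- **Outcomes.** Two of the three outcomes in the hypothesis have no stated convergence analysis.

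**Working it through.** **Inputs.** From the documents: 48 children and a 5% error rate (7.1), three conditions of five days (6.1), day origin at Day 1 (7.2). The documents give no SD, so 48 cannot be reproduced and is used only as an input. Assumed: complete data; daily SD σ of 80–170 kcal; child-by-condition intercept SD i of 0 or 60 kcal at Day 1; child-by-condition slope SD s of 0, 15 or 30 kcal/day.

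**1. Error term.** Let t = day − 1 = 0,…,4, so Σ(t−2)² = 10.

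The variance of one slope that matters for comparing conditions within a child is V = σ²/10 + s².

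A model with random intercept and slope by child only leaves 15 − 2 = 13 df per child: 2 for child-by-condition level, 2 for child-by-condition slope and 9 for daily scatter. (The few df for fixed effects are ignored.) Level variance at Day 3, two days from the origin, is i² + 4s². The model therefore uses W = {σ² + [2·5·(i² + 4s²) + 2·10·s²]/13}/10 in place of V.

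The upper tail of a 2-df chi-square is exp(−x/2). In large samples the nominal 5% test of condition by linear day therefore rejects a true null with probability 0.05^(W/V).

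First row of the table: V = 640 + 900 = 1540; W = [6400 + (36000 + 18000)/13]/10 = 1055; 0.05^(1055/1540) = 12.8%.

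| i | s | σ | V | W | Rejection rate |
|---|---|---|---|---|---|
| 0 | 30 | 80 | 1540 | 1055 | 12.8% |
| 0 | 30 | 170 | 3790 | 3305 | 7.3% |
| 60 | 0 | 80 | 640 | 917 | 1.4% |
| 60 | 0 | 170 | 2890 | 3167 | 3.8% |
| 60 | 15 | 80 | 865 | 1021 | 2.9% |
| 60 | 15 | 170 | 3115 | 3271 | 4.3% |
| 60 | 30 | 80 | 1540 | 1332 | 7.5% |
| 60 | 30 | 170 | 3790 | 3582 | 5.9% |

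Simulation with 48 children agrees: about 8–13% with slopes alone, 1.5–4% with intercepts alone, and 3–8% with both. Testing against child-by-condition variation gives about 5% throughout.

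**2. Linear coefficient.** In y = b0 + b1·t + b2·t², b1 is the tangent at Day 1. The average slope from Day 1 to Day 5 is b1 + 4·b2.

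Write c for the slope at Day 3 (day centred there), so that b1 = c − 4·b2. In units of σ², Var(c) = 1/10 and Var(b2) = 1/14, and the two are uncorrelated. Hence Var(b1) = 0.1 + 16/14 = 1.243, against 0.100 without the quadratic. The ratio of standard errors is √12.43 = 3.5. The Day 1 to Day 5 change is 4c, with variance 1.6 whether or not the quadratic is kept.

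Two hypothetical gaps between conditions, in kcal on Days 1–5:

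- 50, 50, 46, 30, 0: c = (−100 − 50 + 30)/10 = −12.0; b2 = (100 − 50 − 92 − 30)/14 = −5.14; b1 = −12.0 + 20.6 = +8.6; fitted change 4c = −48. The tangent reads as divergence although the gap closes.
- 50, 25, 12, 4, 0: c = (−100 − 25 + 4)/10 = −12.1; b2 = (100 − 25 − 24 − 4)/14 = 3.36; b1 = −12.1 − 13.4 = −25.5; fitted change −48.4. The sign is right, but the tangent is about twice the average slope.

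**3. Menu.** Simulated under a true null with 6–12 classrooms, menu SD 50–100 kcal and daily SD 100–170 kcal, all assumed:

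- Menu omitted, each classroom keeps one menu order in all three periods: 1–4%. Menu effects cancel from the contrast but inflate the residual.
- Menu omitted, orders drawn independently by period: 9–49%. Menu differences then look like slope differences shared by a classroom.
- Menu included: 3.5–6.3% under either scheme.

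Section 6.1 does not say which scheme applies or how many classrooms take part.

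**4. Outcomes.** Section 1.1 has three (vegetables, fruit, energy); the Hypothesis 3 paragraph of 7.2 has one (energy).

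**The case against.** The strongest reply is that the intention is clear. The paragraph asks whether intake in the three conditions converges, and 7.2 opens by saying that outcomes are tested across conditions and days. A condition-by-time term is the natural reading. This stands: a reader might infer that the plan never compares trajectories between conditions, and the text does not support that. The model for Hypotheses 1 and 2 also screens interactions. With day as a factor, however, condition by day has (3−1)(5−1) = 8 df and tests for any pattern, so it does not replace a convergence test.

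It can also be said that varying by child does not exclude variation by child and condition. That is true, since the text is silent. But only the child level is described, and an analyst who follows it literally gets the standard errors in step 1.

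The wording on the linear coefficient is correct if the quadratic is dropped, and the curvature sentence is standard growth-curve language. The problem arises only if the quadratic is kept, and the wrong-sign case is one constructed pattern.

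A reader might add study week to menu as a harmful omission. The documents do not support this. An additive week effect is constant over the five days, so with complete data it cancels from every within-child slope contrast.

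**Conclusion.** The point holds as an incomplete and partly misdescribed analysis of a central hypothesis, and should be corrected before analysis. It is not a flaw in the design.

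The algebra of the linear term and the mismatch in outcomes between 1.1 and 7.2 need no assumed variance. The error-term and menu figures do. With 48 children and the assumed SDs, child-level random terms alone move a 5% test to somewhere between about 1.5% and 13%, depending on which variation is present. The mixed cases run from about 3% to 8%.

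A reader might infer that the plan inflates false positives, perhaps above 20%. The documents do not show this, because they report no child-by-condition variance. Rates that high arise only if slopes are assumed to fan out around Day 3 with no difference in level, whereas the plan's origin is Day 1. The menu effect likewise depends on facts that the documents do not state.

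**What to change.** In the Hypothesis 3 paragraph of 7.2:

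1. Name the condition-by-linear-day test (2 df) as the test of convergence. Follow it with pairwise slope differences and confidence intervals to show direction, because the overall test also detects divergence.
2. Express these as the Day 1 to Day 5 change in the gap, or centre day at Day 3, so that the meaning holds whether or not a quadratic is kept.
3. Include menu as a fixed effect.
4. Add a random intercept and slope by child within condition to those by child.
5. Run the same model for vegetable and fruit intake, or narrow Hypothesis 3 in 1.1 to energy.

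The cost is SAP wording and a few model terms on data already planned, with no extra children. The drawbacks are more variance parameters, possible difficulty in fitting them with five days per condition, and somewhat wider intervals where slopes do vary. At most this is a factor of √(1540/1055) = 1.21 in the cases of step 1.
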